9.7.3 Correlative Study Endpoints

- Association between inherited genetic polymorphisms of functional relevance near or within genes encoding proteins with roles in steroid hormone transport and androgen receptor signaling with changes in metabolic parameters among men treated with androgen deprivation therapy.
- Mean change from baseline in trabecular bone architecture as measured by trabecular bone number (TbN) and trabecular bone volume fraction (BV/TV) after 12 months of androgen deprivation therapy.
- Association between 2D:4D ratio with change in quality of life on androgen deprivation therapy.
- Association between 2D:4D ratio and baseline and percent change from baseline in empathy score.

9.8 Methods for Analysis

Generally, frequency distributions, means, and standard deviations will be used to describe subject demographics and baseline characteristics. Univariate analysis among variables will be assessed using the two-sample t-test, Wilcoxon-rank-sum test, Chi-square test, as appropriate. Statistical significance will be declared based on alpha level of 0.05. For the endpoints with missing less than 25% of values, multivariate imputation using fully conditional specification (R MICE package) will be implemented. For endpoints missing more than 25% of values, the endpoint will be excluded from the final analysis.

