8.1 Percent Body Fat Estimation

Percent body fat will be estimated at baseline and every 3 months with the use of standard bioelectrical impedance monitor (see Appendix 4). Prior studies have demonstrated high reliability and strong correlation with other modalities including DXA scans.

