9.5 Analysis Populations

The primary analysis for the randomized cohort will include all patients who have a body fat % measurement at baseline and at month 12 on study (± 2 weeks). If a patient comes off study prior to obtaining the end of month 12 body fat % measurement, they will not be included in the primary study analysis.

All patients enrolled in the chemohormonal non-randomized cohort who complete C1D1 visit will be included in the analysis of the primary endpoint, the percentage of completed visits in the STAND clinic.

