9.8.1 Analytic Plan for the Primary Objective

Two-sample t-test will be used to compare the mean percent change from baseline in percentage body fat after 12 months of study participation. The changes in percentage body fat across the

different time points will be evaluated using repeated measures analysis of covariance. To further characterize the patterns over the time and investigate the effect of treatment arm assignment, a linear mixed model will be applied with adjusting for stratification factors and covariates including Charlson co-morbidity index score, age, and baseline depression score as measured by PHQ-9. Patients who do not have a baseline or end-of-month 12 percentage body fat measurement, or those that start medications known to affect body fat/body weight during the course of the 12-month study, including metformin, insulin, corticosteroids, mirtazapine, or megestrol, will be excluded from the primary endpoint analysis. In an exploratory analysis, these patients will be retained to assess the impact of STAND clinic participation on changes in percentage body fat over time both before and after initiation of medical management.

For the non-randomized chemohormonal cohort, the point estimate and 95% confidence interval of the percentage of completed STAND clinic visits will be reported.

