9.8.2 Analytic Plan for the Secondary Objectives

Two-sample t test will be used to compare the mean change from baseline to 12 months for the secondary endpoints which hold the normality assumption. For endpoints that do not hold the normality assumption, as well as for ordinal level of measurements, Wilcoxon-rank-sum test will be used. To evaluate the changes in secondary endpoints across the different time points, repeated measures analysis of covariance will be used for continuous endpoints (appropriate transformation will be applied if normality assumption doesn't hold), while repeated measures generalized estimation equation with a cumulative logic categorical will be applied for the ordinal level of measurements. Generalized linear mixed models with adjustment for stratification factors and possible covariates will be applied to further characterize the patterns over the time and investigate the effect of the care type with appropriate link function. Results will be displayed in a graphical fashion. Patients who start medications known to affect endpoint being analyzed (e.g. statins for the lipid panel measurement) will be excluded from the main statistical analysis. In a sensitivity analysis these patients will be retained to assess impact of STAND clinic participation on study outcomes. No adjustment for multiple comparisons will be made for the analysis of the secondary, exploratory objectives.

For patients who cross-over from standard-of-care to participate in the STAND clinic, the mean change from month 12 to month 24 after twelve months of participation in the STAND clinic with respect to the study endpoints will be descriptively reported.

During the follow-up phase of the study, the mean change from completion of STAND clinic participation to 12 months after completion with respect to study endpoints will be descriptively reported.

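### Section 9.8 imputes missing endpoints by MICE while 9.5 and 9.8.1 exclude men without a month-12 value from the primary analysis, with no order of precedence; 9.8 also discards any secondary endpoint with more than 25% missing.

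*Combined protocol and SAP*

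**What the plan says.** Section 9.8 sets two rules for endpoints in general. The first is imputation: "For the endpoints with missing less than 25% of values, multivariate imputation using fully conditional specification (R MICE package) will be implemented". The second is deletion: "For endpoints missing more than 25% of values, the endpoint will be excluded from the final analysis". Neither sentence is limited to secondary endpoints.

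The sections on the primary endpoint say something different. Under 9.5 the primary analysis of the randomised cohort "will include all patients who have a body fat % measurement at baseline and at month 12", and of men who come off study before the month-12 measurement it says "they will not be included in the primary study analysis". Section 9.8.1 repeats the exclusion ("Patients who do not have a baseline or end-of-month 12 percentage body fat measurement, or those that start medications", followed by a list of drugs). It then keeps the excluded men in an exploratory analysis of the clinic's effect "on changes in percentage body fat over time both before and after initiation of medical management".

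For the secondary endpoints, 9.8.2 removes men who start a drug known to affect the endpoint under analysis: "e.g. statins for the lipid panel measurement) will be excluded from the main statistical analysis". A sensitivity analysis retains them. Section 9.8.2 mentions neither imputation nor the 25% cut-off.

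On data collection, 8.1 says: "Percent body fat will be estimated at baseline and every 3 months". Intermediate values will therefore exist for many men who lack a month-12 value.

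**The concern.** There are two separate problems.

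**Primary endpoint.** Taken literally, 9.8 imputes the same men whom 9.5 and 9.8.1 exclude. Nothing ranks the two rules, confines MICE to the secondary endpoints, or labels one result as the sensitivity analysis. A completer result and an imputed result could each be defended from the text after the data are seen. The two can differ: if leaving the study is related to fat gain, and differently so by arm, the completer comparison is biased. The plan has no clear check on this. The exploratory analysis in 9.8.1 is worded around the start of medical management, so it is uncertain whether it covers men who simply have no month-12 value.

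**Secondary endpoints.** The deletion rule plainly applies here. It gives no denominator and does not say whether men removed under 9.8.2 for starting a drug count as missing. It also leaves exactly 25% missing covered by neither sentence. Bone density shows why the denominator matters: 9.7.2 restricts it to men without bone metastases at entry, so with 80 as denominator, ineligible men could be counted as missing. The cut-off is fixed in advance and does not select on the treatment effect. The harm is that collected data go unreported.

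**Working it through.** **Inputs.** From 9.2: 40 men enrolled per arm, 32 evaluable per arm, 20% inevaluable, a control-arm increase of 12% (SD 17%) against no increase with the clinic, and a two-sided two-sample t-test at 0.05. From 9.8: the 25% cut-off. From 9.7.2: 9 metabolic + 2 bone + 6 quality-of-life items = 17 secondary items.

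**The plan's own figure.** The power of the t-test (noncentral t) with 32 per arm is 79.8% at an effect size of 0.71, and 79.4% at 12/17 = 0.706. Inflating for loss gives 32 / (1 − 0.20) = 40 per arm. The stated sample size reproduces and is not in question.

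**Primary analysis set under each rule.** Assume that all inevaluable men lack a month-12 value.
- Missing: 80 × 0.20 = 16, which is 20% and therefore under 25%.
- Under 9.8: 80 men analysed, 16 of them imputed.
- Under 9.5 and 9.8.1: 80 − 16 = 64 completers, 32 per arm.

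**Where deletion starts.** 0.25 × 80 = 20, so more than 25% means 21 or more missing, which leaves 80 − 21 = 59 men (30 and 29).

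| Men per arm | Difference detectable at 80% power | Power at 12/17 |
|---|---|---|
| 32 / 32 | 0.711 SD | 79.4% |
| 30 / 29 | 0.742 SD | 76.0% |

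An endpoint just past the cut-off has lost little precision. This says nothing about bias.

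**Chance of crossing the cut-off.** Exact binomial, P(X ≥ 21) with n = 80 and missingness independent between men:

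| True missing rate | P(21 or more of 80) |
|---|---|
| 10% | 0.003% |
| 15% | 0.6% |
| 20% | 10.7% |
| 25% | 44.0% |

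These are probabilities for one item. A man who leaves before month 12 lacks every month-12 item, so items would tend to cross together. The same probabilities apply to the primary endpoint only on the less likely reading that 9.8 governs it.

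**Can the choice change the primary result?** An illustrative simulation used assumptions that are not in the plan: 40 per arm, SD 17, and a correlation of 0.5 to 0.8 between month 9 and month 12. Dropout in the clinic arm rose with month-9 fat gain (log-odds slope 1 per SD), giving about 20% missing in control and 24% in the clinic arm. Regression imputation from arm and month-9 value stood in for the MICE point estimate.

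| True difference | Completers | Imputation |
|---|---|---|
| −12 | −13.7 to −14.8 | about −12 |
| 0 | −1.8 to −2.8 | about 0 |

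With dropout unrelated to outcome, both methods were unbiased. The scenario favours imputation by construction, because dropout depends only on an observed value. It shows that the two rules can disagree, not by how much they will in this trial.

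**The case against.** Two explicit sections exclude the same men, and 9.2 sizes the trial on evaluable patients. An imputed primary result would contradict both sections, so the freedom to choose is limited and the first part needs only a sentence. That is largely right. The specific sections are the likelier authority, but the plan leaves it to be inferred.

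The sensitivity analysis may already be there. Section 9.8.1 plans a repeated-measures analysis and a linear mixed model, which can use men with 3-monthly values but no month-12 value. Its exploratory analysis also refers back, grammatically, to all the excluded men. This reading is possible, but the text does not settle it: the exclusion could extend to the mixed model, and the exploratory analysis is described in terms of starting medication.

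The deletion rule is pre-specified, applies to endpoints the plan calls exploratory, and may never operate. Inevaluable is not defined and may include men who start a listed drug, so true missingness could be well below 20%. The 44% figure needs missingness above the plan's whole allowance. These points stand as limits on likelihood. They do not give a reason to discard an endpoint that keeps nearly full precision. The bone-density denominator, smaller than 80, adds to the ambiguity.

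**Conclusion.** The concern holds. The plan has two rules for a missing month-12 body-fat value and does not rank them. It also has a deletion rule that, followed as written, would leave collected secondary endpoints unanalysed.

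For the primary endpoint the difference is 64 completers against 80 men with 16 imputed, assuming that every inevaluable man lacks month-12 data. On its own the missing precedence sentence is close to a clarification. What makes it worth correcting is that completers can be biased and that no analysis clearly tests for this.

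For the secondary endpoints, with 80 as an assumed denominator and equal loss by arm, deletion begins when 59 men still have data. The probability that an item crosses is negligible at 10% missing, 0.6% at 15% and about 11% at 20%.

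The textual finding is firm. Its practical size depends on dropout rates and mechanisms that the documents do not give. The change should be made; the sample size is unaffected.

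**What to change.** 1. State in 9.8 that the completer two-sample t-test is the primary analysis, as 9.5 and 9.8.1 describe and 9.2 is powered for, and limit the MICE sentence accordingly.
2. Add one pre-specified sensitivity analysis of all randomised men with a baseline body-fat value, using the 3-monthly measurements. Name the method in advance, either the mixed model or MICE, and say whether men who start a listed drug are included.
3. Remove the rule that drops endpoints above 25% missing. Report every endpoint with its missing fraction by arm. The undefined case of exactly 25% then disappears.

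The exclusion of medication starters from the primary analysis is left as it is.

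**Cost.** A protocol amendment under 10.4 is needed, but no new visits, data or methods. The added analysis assumes data are missing at random, and secondary endpoints with heavy missingness would need a caveat when reported.

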9.8.1 Analytic Plan for the Primary Objective

Two-sample t-test will be used to compare the mean percent change from baseline in percentage body fat after 12 months of study participation. The changes in percentage body fat across the

different time points will be evaluated using repeated measures analysis of covariance. To further characterize the patterns over the time and investigate the effect of treatment arm assignment, a linear mixed model will be applied with adjusting for stratification factors and covariates including Charlson co-morbidity index score, age, and baseline depression score as measured by PHQ-9. Patients who do not have a baseline or end-of-month 12 percentage body fat measurement, or those that start medications known to affect body fat/body weight during the course of the 12-month study, including metformin, insulin, corticosteroids, mirtazapine, or megestrol, will be excluded from the primary endpoint analysis. In an exploratory analysis, these patients will be retained to assess the impact of STAND clinic participation on changes in percentage body fat over time both before and after initiation of medical management.

For the non-randomized chemohormonal cohort, the point estimate and 95% confidence interval of the percentage of completed STAND clinic visits will be reported.

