9.2 Determination of Sample Size and Study Power

The sample size estimate is based upon the primary endpoint of the study, the mean percent change in percentage body fat from baseline to 12 months. Based on prior prospective longitudinal studies, it is estimated that men receiving ADT and standard-of-care physician counseling regarding expected toxicities will experience a mean 12% (sd = 17%) increase in percentage body fat after 12 months of ADT [13]. If men participating in the STAND clinic, with individualized exercise/nutrition counseling and longitudinal assessment, have, on average, no increase in percentage body fat mass after 12 months of hormone therapy, this would warrant further evaluation of a multi-disciplinary clinic in a larger randomized clinical trial with long-term endpoints of interest, including incidence of diabetes and potentially cardiovascular disease. An enrollment target of 32 evaluable patients per arm will provide power of 80% to detect an effect size of 0.71 in the difference in mean percent change from baseline to 12 months in percentage body fat mass between the two arms, using a two-sample t test and a two-tailed level of significance = 0.05. The total planned accrual is 40 patients per arm accounting for an inevaluable rate of 20%.

A sample size of 20 patients is chosen for the non-randomized chemohormonal cohort to establish the feasibility of a multi-disciplinary clinic in this patient population. The primary endpoint for this pilot cohort is the percentage of completed STAND clinic visits, with a target goal of 80%. A sample size of 20 patients (13 visits per patient; 260 visits in total) provides 17.5% precision to determine the percentage of completed visits at 95% confidence.

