9.3 Interim Analysis

Interim analysis will be performed after 33% of the planned sample size of randomized patients complete 12-month care. To preserve the overall type I error rate at < 0.05 , the Lan-DeMets spending function will be used to allocate nominal alpha-levels at the interim and final analyses. The efficacy stopping boundaries for the primary efficacy endpoint at the interim and final analyses are $p < 0.026$ and $p < 0.474$, respectively.

An interim analysis for the non-randomized cohort will be performed after 10 patients have been enrolled on the STAND clinic for a minimum of 6 months. If the percentage of completed STAND visits is less than 60%, the study schedule will be altered to ensure higher rates of patient adherence to the clinic schedule.

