10.4 Changes in the Protocol

Once the protocol has been approved by the UCSF Committee on Human Research (CHR), any changes to the protocol must be documented in the form of an amendment. The amendment must be signed by the Investigator and approved by PRC and the CHR prior to implementation.

If it becomes necessary to alter the protocol to eliminate an immediate hazard to patients, an amendment may be implemented prior to CHR approval. In this circumstance, however, the Investigator must then notify the CHR in writing within five (5) working days after implementation.

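### The primary t-test is sound as a choice of test but ignores the randomization strata and baseline body fat; adjusting for them is an optional, modest gain in efficiency

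*Combined protocol and SAP*

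**What the plan says.** **Primary test.** Section 9.8.1: "Two-sample t-test will be used to compare the mean percent change from baseline in percentage body fat after 12 months of study participation". Section 9.2 sizes the trial for the same endpoint, "using a two-sample t test and a two-tailed level of significance = 0.05".

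**Other planned analyses of body fat (9.8.1).** Changes over the visits come next: "different time points will be evaluated using repeated measures analysis of covariance". The covariates of that analysis are not named. Then "a linear mixed model will be applied with adjusting for stratification factors and covariates including Charlson co-morbidity index score, age, and baseline depression score", the last measured by PHQ-9; one stated purpose of this model is to "investigate the effect of treatment arm assignment". Neither analysis is the primary comparison, and neither names baseline percentage body fat.

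**Data available.** Section 9.5 limits the primary analysis to "all patients who have a body fat % measurement at baseline and at month 12 on study". Section 7.3 stratifies randomization by prior ADT duration and BMI, so all three covariates exist for every man analysed.

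**Interim look.** Section 9.3: "Interim analysis will be performed after 33% of the planned sample size of randomized patients complete 12-month care". It prints boundaries of p < 0.026 (interim) and p < 0.474 (final).

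**Strata.** Section 7.3 speaks of six strata but lists two factors with two levels each. BMI is split at < 30 / ≥ 30 in the synopsis and at ≤ 30 / > 30 in 7.3.

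**Questionnaire scores.** The objectives and endpoint lists (synopsis, 2.2.2, 3.2.2, 9.7.2) and the 2D:4D comparison in 9.8.3 use percent change. Section 9.8.2 tests mean change, without the word percent.

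**The concern.** When randomization is stratified on factors that predict the outcome, the design removes most of the stratum imbalance between arms, but the t-test's standard error still contains the stratum variance. The test is then conservative. Baseline body fat, if it predicts percent change, likewise leaves variance in the comparison that could be removed at no data cost. The plan has no surplus power to give away, and the model that uses the strata does not decide the trial.

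What is at stake is precision: at most a few points of power over the range examined. The strata conflicts matter because the planned mixed model already needs stratum terms coded in one way.

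**Working it through.** **Inputs.** From 9.2: difference 12 points (12% against no increase), SD 17%, 32 evaluable per arm, two-sided 0.05, 20% inevaluable. The variance share R² explained by baseline body fat and the strata is not in the documents. It is assumed, from 0 to 0.10 only, because percent change already divides by baseline and because BMI stratum and baseline body fat may overlap.

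**1. The plan's own figure.** Noncentral t, noncentrality d·√(n/2) = d·√16, df = 62:
- d = 0.71: noncentrality 2.84, power 79.8% (stated: 80%).
- d = 12/17 = 0.706: noncentrality 2.82, power 79.4%.
- Enrolment: 32/(1 − 0.20) = 40 per arm, as stated.

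The figures reproduce.

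**2. Adjusted analysis, balanced covariates.** Effect d/√(1 − R²), df = 64 − 5 = 59:

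| R² | d/√(1 − R²) | Power |
|---|---|---|
| 0 | 0.706 | 79.3% |
| 0.03 | 0.717 | 80.5% |
| 0.05 | 0.724 | 81.3% |
| 0.10 | 0.744 | 83.3% |

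**3. Allowing for chance imbalance.** Simulation with 80 men, 20% random loss, four strata from two 50/50 factors, permuted blocks of 4 (block size is not given, so assumed), R² split equally between strata and baseline, 180,000 runs per row. The interim rows use p < 0.026 and no loss. Section 9.3 does not say whether its 33% refers to 80 men (0.33 × 80 ≈ 26) or to the 64 evaluable men (0.33 × 64 ≈ 21), so both are shown.

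| Look | R² | t-test | Adjusted |
|---|---|---|---|
| Final, α 0.05 | 0 | 79.0% | 78.0% |
| | 0.03 | 79.4% | 79.3% |
| | 0.05 | 79.4% | 80.1% |
| | 0.10 | 79.5% | 82.2% |
| Interim, 26 men | 0 | 30.0% | 27.9% |
| | 0.05 | 29.9% | 29.4% |
| | 0.06 | 29.7% | 29.8% |
| | 0.10 | 29.6% | 31.1% |
| Interim, 21 men | 0 | 23.7% | 21.5% |
| | 0.07 | 23.4% | 23.1% |
| | 0.10 | 23.3% | 23.9% |

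Adjustment breaks even at R² of about 0.03 at the final look and about 0.06 to 0.08 at the interim.

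**4. Type I error.** With perfect stratum balance, the true variance of the difference is (1 − R²) times what the t-test assumes, so null rejection is about 2Φ(−1.96/√(1 − R²)): 4.4% at strata R² 0.05 and 3.9% at 0.10. Simulated at the final look with incomplete blocks and loss (240,000 runs), at strata R² 0 / 0.05 / 0.10:
- t-test: 5.0% / 4.6% / 4.2%.
- Adjusted: 5.0% throughout.

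**5. Boundary check.** At an information fraction of 0.33, the printed pair 0.026 and 0.474 gives an overall type I error of about 48%. If 0.0474 was meant (an assumption), the pair gives about 6.6%, and final-look power of the t-test is 78.7% instead of 79.4%.

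**6. Strata.** 2 × 2 = 4, not six. The two BMI definitions differ only at exactly 30.

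**7. Zero baselines.** PHQ-9 and HFRDIS items start at 0 (Appendix 2), and the HFRDIS tells men without hot flashes to mark zero. Section 4.1 admits men who have not yet started ADT. A percent change from 0 is undefined.

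**The case against.** **This is a preference, not a defect.** The test matches the sample size, the documents give no R², and the gain could be nil or slightly negative. All of that stands, and it is why the point is optional.

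**The plan already adjusts.** A reader might infer that the plan has no covariate adjustment. It does: the mixed model includes the strata and examines the effect of arm, and its covariate list is open-ended, so baseline body fat is not ruled out. What remains is that the deciding test uses none of these variables and that baseline body fat is never specified.

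**Changing the primary test mid-trial has a credibility cost.** This stands. Footnote e of the study schedule shows that men are already enrolled, and the documents do not say whether the interim look has taken place. If it has, the case for changing the primary test lapses.

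**Section 9.8.2 may settle the zero-baseline problem.** A reader might take its wording as absolute change, which would leave the between-arm questionnaire tests unaffected. The documents do not establish that. The objectives and every endpoint list say percent change for the same scales, and 9.8.3 itself refers to a percent change simply as a change. The between-arm comparison may be affected as well as the 2D:4D one.

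**Conclusion.** The point holds as an efficiency choice worth considering. Over R² of 0 to 0.10, adjustment moves final-look power by about −1 to +3 points in simulation (79.3% to 83.3% against 79.4% by formula). It brings null rejection back to 5% where the t-test would fall to about 4%. These sizes rest on the assumed R², the assumed block size and random loss.

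Two stronger readings are not supported. One is that the t-test is wrong or inflates false positives: it does not, and any departure is on the conservative side. The other is that adjustment will rescue a meaningful amount of power: nothing in the documents fixes R², and below about 3% the t-test does as well or better.

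The conclusion covers the choice of test only. It does not endorse the primary analysis as a whole, which also excludes men who start listed medications after randomization or lack a month-12 value (9.5, 9.8.1).

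The strata count, the BMI cut, the final boundary and the percent-change wording are text conflicts that need correction whichever test is kept.

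**What to change.** **Primary model.** By amendment before interim data are analysed, make the primary analysis a linear model of percent change in percentage body fat on arm, baseline percentage body fat, ADT-duration stratum and BMI stratum, used at both looks. Report the t-test as supportive. The endpoint (9.7.1) and the 12-point effect (9.2) do not change. If the team expects these covariates to explain less than about 3% of the variance, keeping the t-test is defensible; record that decision.

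**Before either look is run.** Correct the final boundary in 9.3 by recalculating it together with the interim boundary, since moving the decimal point alone would not restore 0.05. Reconcile six strata with the two binary factors, and choose one BMI cut, so that the strata are coded one way.

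**Questionnaire scales.** Use absolute change for scales that can be 0 at baseline, and say so in the synopsis objectives and endpoints, 2.2.2, 3.2.2, 9.7.2, 9.8.2 and the 2D:4D paragraph of 9.8.3.

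**Cost.** No new data and one model statement. Three degrees of freedom are lost (59 instead of 62), with about 1 point of power at the final look and 2 at the interim if the covariates explain nothing. Section 10.4 applies: "The amendment must be signed by the Investigator and approved by PRC and the CHR prior to implementation".

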7.1 Study Schedule

	Pre-Study/ Screening (within 6 weeks of Day 1 of Study)	Day 1 Study Visit	End of Every Month (+/- 2 weeks)	End of Every 3 Months (+/- 2 weeks)	End of Month 12 Study Visit (+/- 2 weeks)	Follow Up Visit ¹ (6 months after completion of STAND clinic)
Physical Exam with Health Care Provider (Both study arms)	X	X		X	X	X
LHRH Analogue ^a		X		X		
Exercise, Nutrition, Symptom Management counseling ^b		X	X			
Educational Modules (STAND clinic arm only)		X	X			
Counseling, review tests and questionnaires				X	X	X
Informed Consent	X					
Randomization	X					
Demographics	X					
Past Medical History	X					
Concomitant Medications ⁱ	X	X		X	X	
QOL/empathy Questionnaires ^c		X		X	X	X
Co-morbidity Assessment ^d	X					
Ratio of 2 nd to 4 th digit finger length ^e	X					
Weight/Body Mass Index/Percent Body Fat ^f	X	X		X	X	X
ECOG Performance		X		X	X	

DXA Scan ^f	X				X	
HRpQCT (optional) ^h	X				X	
Serum PSA ⁱ	X	X		X	X	X
Serum testosterone		X ^j			X	X
Serum 25-(OH) vitamin D level		X		X	X	
Fasting glucose/lipid panel, HgbA1c, insulin level		X		X	X	X
Hemoglobin A1c		X		X	X	X
Plasma/serum for banking ^k		X		X	X	X
PBMCs for germline polymorphisms (optional) ^k		X				

a. Patients who have started ADT prior to study enrollment will be kept on same schedule for next dose of LHRH analog and provider visit while on study. On study patients will receive LHRH agonist every 3 months (+/- 1 week), on same day as health care provider visits whenever possible.

b. Patients randomized to the STAND clinic will visit with one of three specialties (exercise, nutrition, symptom management) at each monthly visit. The total number of visits with each specialty will be four on an every 3-month basis. The rotation of the schedule of providers may be adjusted depending upon availability of provider and patient. Patients randomized to the usual care study arm will be referred to nutrition, exercise, and symptom management services upon patient request or as deemed necessary by health care provider.

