During the course of visit with symptom management service, patients physical and psychosocial issues will be addressed by trained health care provider. Counseling and medical management will be provided.

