7.8 Concomitant Medications

Concomitant medications will be recorded at each study visit. The addition of medications to manage fasting blood glucose, lipids, bone density, or blood pressure will be allowed and at the discretion of the individual treating physician.

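### Sections 9.5 and 9.8.1 define different primary analysis sets; 9.8.1 also drops men who start weight-affecting drugs after randomisation, which the assigned arm can plausibly influence

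*Combined protocol and SAP*

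**What the plan says.** Section 9.5 (Analysis Populations) states: "The primary analysis for the randomized cohort will include all patients who have a body fat % measurement at baseline and at month 12". The only men it removes are those who come off study before the month-12 measurement; of them it says "they will not be included in the primary study analysis".

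Section 9.8.1 names the month-12 two-sample t-test as the primary comparison. It then excludes from the primary endpoint analysis men missing either measurement and, in the same sentence, "those that start medications known to affect body fat/body weight during the course of the 12-month study". Metformin, insulin, corticosteroids, mirtazapine and megestrol are given as examples, not as a closed list. The excluded men return only in an exploratory analysis of "changes in percentage body fat over time both before and after initiation of medical management".

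Three other provisions bear on who starts a drug:

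- **STAND arm.** Note b to the Section 7.1 schedule says of the exercise, nutrition and symptom services: "The total number of visits with each specialty will be four on an every 3-month basis". Section 7.5 says of the symptom-service visit: "Counseling and medical management will be provided".
- **Usual care.** Under the same note b, these men "will be referred to nutrition, exercise, and symptom management services upon patient request or as deemed necessary by health care provider".
- **Both arms.** Under Section 7.8, added drugs for glucose, lipids, bone density or blood pressure "will be allowed and at the discretion of the individual treating physician".

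**The concern.** There are two problems.

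First, two analysts working from 9.5 and 9.8.1 would run the primary test on different men. If this is settled after the data are seen, the primary result depends on that choice.

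Second, the 9.8.1 set is chosen on something that happens after the arm is known. The arms differ in scheduled contact with a service that provides medical management, so they may differ in how many men start a listed drug, or in which men do. The groups compared would then no longer be the randomised groups with month-12 data. Because the drug list is illustrative and no minimum duration or adjudication rule is given, membership of the set is also partly a post-randomisation judgement.

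If drug starters are lost on top of the men already allowed for as inevaluable, power falls as well.

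**Working it through.** **1. The two sets side by side.** All cases are randomised men.

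| Man | Section 9.5 | Section 9.8.1 |
|---|---|---|
| Both measurements, no listed drug started | in | in |
| Both measurements, listed drug started | in | out |
| Month-12 value missing | out | out |

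The second row is the contradiction.

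**2. The plan's own sample size (Section 9.2).** Inputs: mean increase of 12% with usual care and 0% with STAND, SD 17%, two-sided 0.05, 32 evaluable per arm, 20% inevaluable.

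- Effect size: 12/17 = 0.706, stated as 0.71.
- Power of the t-test at 32 per arm: 79.8% for 0.71 and 79.4% for 12/17, against 80% stated.
- Enrolment: 32/(1 − 0.20) = 40 per arm.

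The stated figures reproduce.

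**3. Possible bias.** The documents give no drug-start rate and no link between drug start and fat gain, so every rate and correlation below is an assumption. Model: no true effect, SD 17, 32 men per arm before exclusion. A latent propensity to start a drug has correlation ρ with the 12-month change, and the top fraction p of each arm is removed.

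- c = z(1 − p), λ = φ(c)/(1 − p)
- Shift in the retained mean = −ρ × 17 × λ
- Retained variance = 17² × (1 − ρ²(cλ + λ²))
- Retained n = 32(1 − p)
- Bias = STAND shift minus usual-care shift; type I error from the noncentral t

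Worked case, ρ = 0.5, STAND 20%, usual care 5%:

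- STAND: λ = 0.350, shift = −0.5 × 17 × 0.350 = −2.97, variance 258.9, n = 25.6.
- Usual care: λ = 0.1086, shift = −0.92, variance 275.2, n = 30.4.
- Bias = −2.97 + 0.92 = −2.05 points, and 2.05/12 = 17% of the planned difference.
- SE = √(258.9/25.6 + 275.2/30.4) = 4.38; type I error 7.5%.

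| ρ | Start rates, STAND vs usual care | Bias (points) | Type I error |
|---|---|---|---|
| 0.5 | 10% vs 10% | 0.0 | 5.0% |
| 0.3 | 10% vs 5% | −0.4 | 5.1% |
| 0.3 | 20% vs 10% | −0.8 | 5.3% |
| 0.3 | 20% vs 5% | −1.2 | 5.8% |
| 0.5 | 10% vs 5% | −0.7 | 5.3% |
| 0.5 | 20% vs 10% | −1.3 | 6.0% |
| 0.5 | 20% vs 5% | −2.0 (−2.05 before rounding) | 7.5% |
| 0.7 | 20% vs 10% | −1.8 | 7.2% |
| 0.7 | 20% vs 5% | −2.9 | 10.3% |

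A negative bias favours STAND. Reversing either the rates or the sign of ρ reverses it. Equal 10% rates still give 1.0 point if ρ is 0.5 in one arm and 0.2 in the other. A simulation of 200,000 trials agreed with the closed form (2.04 points and 7.4% for the worked case). A different selection model, with the chance of starting logistic in the 12-month change, gave the same pattern: 1.4 to 2.0 points for 20% vs 10%, and 2.1 to 3.1 points for 20% vs 5%.

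**4. Possible loss of power.** Section 9.2 does not say whether the 20% covers drug starters. If it does, nothing is lost. If a further 10% are excluded, n = 32 × 0.90 = 28.8 per arm and power is 74.9% at 12/17. If a further 20% are excluded, n = 25.6 and power is 69.7%.

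**The case against.** The strongest reply is that arm influence is inferred. The documents do not say STAND prescribes any listed drug. Section 7.8 makes no distinction by arm. Both arms have 3-monthly provider visits with fasting glucose and hemoglobin A1c, so the most visible trigger for a glucose-lowering drug is the same in each. Usual-care men can reach the symptom service without restriction. This stands as a limit on how large the bias is likely to be. It does not remove the scheduled difference in contact with that service, and it does not touch the contradiction.

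The illustrative bias is also small at modest correlations and modest rate differences, as the ρ = 0.3 rows show. That is correct, so the figures alone would not carry the point.

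It can further be said that 9.8.1 refines 9.5, that excluding drug starters is a prespecified way to isolate counselling in a preliminary phase 2 trial, and that an analysis retaining these men is planned. The first reading fails because 9.5 says all men with both measurements are included. The second is a legitimate scientific question, but a sensitivity analysis can answer it without giving up the randomised comparison. The third helps little: the retained analysis is exploratory, looks at change around drug initiation, and is not stated to be the month-12 t-test.

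Finally, because one sentence of 9.8.1 excludes missing-measurement men and drug starters together, the 20% allowance may well cover both. The power loss is therefore conditional.

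**Conclusion.** The concern holds and must be fixed before analysis. The plan has two incompatible primary sets, and one of them selects men on an event after randomisation that the arm can plausibly affect. Neither part depends on an assumption about rates.

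The size and direction of bias cannot be determined from the documents. Over the unequal-rate cases tabulated it runs from 0.4 to 2.9 points, with type I error from 5.1% to 10.3%. It is zero when start rates and selection are the same in both arms. Power falls from 79% to 75% only if a further 10% of men are excluded beyond the 20% allowance.

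Section 9.8.2 is a lesser matter. It makes a similar exclusion the main analysis for secondary endpoints, but 9.5 sets no secondary population, so nothing is contradicted, and a sensitivity analysis retaining these men is already planned.

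**What to change.** 1. State the same primary set in 9.5 and 9.8.1: the month-12 two-sample comparison of randomised men regardless of drugs started after randomisation. Delete the drug-start clause from the exclusion sentence in 9.8.1.
2. Make the analysis without drug starters a labelled sensitivity analysis, with a closed drug list fixed in advance, and report drug starts by arm.
3. Secondary: in 9.8.2, swap the main and sensitivity analyses.
4. Related: say in 9.5 whether the imputation rule in 9.8 for endpoints with less than 25% missing applies to the primary endpoint. Without this, step 1 is still not a full as-randomised analysis, because men without a month-12 value remain excluded.

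The cost is small. Section 9.5 already describes the set and 9.8.1 already names the test, so the primary change is the removal of one clause. Section 7.8 has concomitant medications recorded at each visit, so no new data are needed, and 32 evaluable and 40 enrolled per arm stand. The trade-off is that the primary estimate will include any effect of added drugs and will not isolate diet and exercise counselling; the sensitivity analysis addresses that question, subject to the selection described above.
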